3.2 Sample Size

Under traditional 3+3 design model, Part A may enroll between 12 and 24 patients across 4 dose cohorts (3 or 6 active patients per cohort), depending upon what toxicities are observed. No formal hypothesis testing is planned for Part A. In Part B, the total sample size of 24 patients (n=18 KAN-101; n=6 PBO) across 3 dose cohorts (6 active and 2 PBO patients per cohort) was chosen to allow for a comparison of safety, PK, and PD between KAN-101 and PBO. A sample size of 6 active patients per cohort in Part B allows for an 0.80 power to detect a treatment-related AE occurring at an event rate of 0.25.

Patients in Part A may be replaced if they do not receive the full dose of study drug or do not complete the D8 visit, as long as the discontinuation was not due to a DLT assessed to be related to study drug.

Patients in Part B may be replaced if they do not receive the full 3 doses of study drug or do not complete the D21 visit, as long as the discontinuation was not due to a DLT assessed to be related to study drug.

3.3 Assignment to Cohort

Once a patient has met all entry criteria they will be enrolled in the study. In Part A, patients will be assigned to receive open-label KAN-101 at a dose level based on the next available spot in the cohort(s) currently being enrolled. In Part B, the first 2 eligible patients within each cohort will be randomized in a 1:1 ratio to receive either KAN-101 or PBO. After completion of the sentinel dosing, the remaining 6 patients in each cohort will be randomized 5:1 to receive KAN-101 or PBO.

3.4 Endpoints

3.4.1 Primary Endpoints (Part A and Part B)

Incidence and severity of treatment-emergent adverse events (TEAEs) as assessed by the Common Terminology Criteria for Adverse Events (CTCAE) v5.0 or higher.

3.4.2 Secondary Endpoints (Part A and Part B)

Plasma concentrations and PK parameters of KAN-101.

3.4.3 Exploratory Endpoints (Part B only)

CCI

3.5 Assessments

3.5.1 Safety Assessments

Safety and tolerability of KAN-101 will be assessed by AE and other safety assessments as detailed in Appendix 6.1 [Table 8](#) (Part A) and [Table 9](#) (Part B). All patients in Part A will have

a final Follow-Up at D21 (± 1), 20 days after the single administration of KAN-101. All patients in Part B will have a final Follow-Up phone call at D28 (± 3), approximately 20 days after the final administration of KAN-101 on D7.

3.5.1.1 Adverse Events (AE)

All AEs from the time of signing of Informed Consent Form (ICF) through the final Follow-Up Visit/phone call will be collected. Adverse events will be coded using the Medical Dictionary for Regulatory Activities (MedDRA) Version 23.1 (MedDRA Sep 2020) or higher. Ongoing AEs considered at least possibly related to KAN-101 treatment should be followed until resolution, return to baseline, or are considered stable or chronic.

AE:

An AE is defined as any untoward medical occurrence associated with the use of a drug, or with study participation, whether or not consider related to study treatment.

TEAE:

TEAEs are defined as AEs that emerge or worsen in the period from the first dose of study treatment to the final Follow-Up Visit/phone call after the last dose study drug.

The incidence and severity of TEAEs as assessed by the CTCAE v5.0 or higher is considered the primary endpoint. TEAEs that occur before and after gluten challenge will also be examined separately and defined as in section 4.8.1.

DLT:

A dose-limiting toxicity (DLT) for Study KAN-101-01 is defined as any \geq Grade 3 AE assessed as related to KAN-101 or Grade 2 AE assessed as related to KAN-101 not resolving within 14 days. DLTs do not include those AEs attributable solely to intercurrent illness or other concomitant medications.

AE Severity:

The National Cancer Institute Common Toxicity Criteria Adverse Event (NCI-CTCAE) version 5.0 or higher will be used to grade the severity of all AEs, whether or not they are considered related to KAN-101. Toxicities that are not specified in the NCI-CTCAE will be defined as follows:

- Grade 1: Mild; asymptomatic or mild symptoms; clinical or diagnostic observations only; intervention not indicated
- Grade 2: Moderate; minimal, local or noninvasive intervention indicated; limiting age-appropriate instrumental activities of daily living (ADL)
- Grade 3: Severe or medically significant but not immediately life-threatening; hospitalization or prolongation of hospitalization indicated; disabling; limiting self-care ADL
- Grade 4: Life-threatening consequences; urgent intervention indicated
- Grade 5: Death related to AE

AE Causality:

Relationship to the study drug for all AEs will be assessed as “drug related” (Possible, Probable, Definite) or “not drug related” (None, Remote).

Impact of COVID-19:

Pandemic related Impact of COVID-19 data will be assessed, detailing the category of impact (example: Missed Visit, Missed Assessment, Early termination, Screen Failure, Adverse Event, Withdrawal of consent, Death, Replacement subject) based on data collection.

3.5.1.2 Other Safety Assessments

Additionally, safety will be also be examined by the following assessments:

- Clinical laboratory evaluations
- Physical examination
- Vital signs
- Prior and concomitant medications and procedures
- Incidental gluten exposure
- Medications for infusion reactions
- Study drug administration

3.5.1.2.1 Clinical Laboratory Evaluation

All statistical analyses of laboratory values will be performed using International System units. The Clinical laboratory parameters and tests to be analyzed locally or centrally by a certified laboratory with corresponding laboratory normal ranges are:

- Serum Chemistry: Blood urea nitrogen, creatinine, glucose, aspartate aminotransferase (AST), alanine aminotransferase (ALT), alkaline phosphatase (ALP), bilirubin (total and direct), electrolytes (sodium, chloride, bicarbonate, potassium), amylase, lipase, albumin, magnesium, calcium, and phosphorus
- Hematology: White blood cell (WBC) count, hemoglobin, hematocrit, Platelet (PLT) count, and WBC differential
- Coagulation: Prothrombin time, partial thromboplastin time or activated partial thromboplastin time, and international normalized ratio
- Complete urinalysis with qualitative analysis for protein (dipstick)
- Virus Serology: Human immunodeficiency virus (HIV), hepatitis B (HBV) (HBsAg, anti-HBc and anti-HBs), and hepatitis C (HCV) testing (Screening only)
- Serum pregnancy test will be performed at screening for women of child-bearing potential (WCBP). Serum or urine pregnancy testing for all WCBP will be performed prior to each dose.

The following laboratory tests will be performed centrally at Screening only:

- HLA DQ2.5 and HLA DQ8 testing
- Transglutaminase (tTG) and deaminated gluten peptides (DGP) IgA/IgG

For tTG, a result of <2xULN will be considered negative or weak positive. For DGP, a result of <30 U/mL will be considered negative or weak positive.

For re-screening, the HLA does not need to be repeated and the tTG and DGP antibody tests should only be repeated if >3months have elapsed from end assessment.

Unscheduled assessments should be performed as clinically indicated. For any out-of-range laboratory findings during screening, repeat laboratory testing may be performed at the discretion of the Investigator. Abnormal laboratory findings at screening should be recorded as medical history only if considered clinically significant (CS).

Investigators will assess whether the values outside the clinical reference range are clinically significant and these will be reported as abnormal NCS or abnormal CS.

- Clinically significant abnormal laboratory values will be recorded by the Investigator as AEs.
- The abnormal values will be flagged with 'LOW' for values below the lower limit of the local clinical reference range and 'HIGH' for values above the upper limit of the local clinical reference range and included in the listings.

3.5.1.2.2 Physical Examination

The physical exam (PE) will be conducted at Screening and as clinically indicated, including for early terminated subjects. The PE includes an assessment of general appearance, skin, head, neck, throat, lymph nodes, cardiovascular, neurological, thyroid, musculoskeletal / extremities, respiratory, abdomen, height (screening only) and weight (screening only).

3.5.1.2.3 Vital Signs

Vital signs will include temperature, pulse rate and blood pressure (BP) (sitting for 5 minutes). If vital signs need to be repeated during a single visit, assessments should be conducted approximately 5 minutes apart.

Any new CS change from baseline should be recorded as an AE.

3.5.1.2.4 ECG

All electrocardiograms (ECGs) will be standard resting 12-lead ECGs performed after the patient has been supine for at least 5 minutes. ECG data will be presented.

3.5.1.2.5 Prior and Concomitant Medications and Procedures

At screening, concomitant medications will be recorded. Assessment of any change in concomitant medications, or procedures since the last visit will occur at all further patient visits through the final Follow-Up Visit. Concomitant medications will be coded using the World Health Organization Drug Dictionary drug (WHO Drug Global Sep 2019) and will be presented by WHO-DD Anatomical Therapeutic Chemical (ATC) therapeutic Level 4 classification and preferred term (PT). Below rules will be applied to decide if the medications and procedures are prior, concomitant or both.

- Medications that start and stop prior to the first dose of study medication will be classified as prior only.
- If a medication starts before the date of first dose of study medication and stops on or after the date of first dose of study medication, then the medication will be classified as both prior and concomitant.
- Medications will be classified as concomitant only if they have a start date on or after the first dose of study medication.
- If medication start and/or stop dates are missing or partial, the dates will be imputed (section 4.4.3.2).
 - Medications will be assumed to be concomitant only, unless there is clear evidence (through comparison of partial dates) to suggest that the medication started prior to the single dose of study medication.

- If there is clear evidence to suggest that the medication started prior to the single dose of study medication, the medication will be assumed to be both prior and concomitant, unless there is clear evidence to suggest that the medication stopped prior to the single dose of study medication.
- If there is clear evidence to suggest that the medication stopped prior to the single dose of study medication, the medication will be assumed to be prior only.

3.5.1.2.6 Incidental Gluten Exposure

Assessment (date and source) of any incidental gluten exposure will be captured at all study visits.

3.5.1.2.7 Medications for Infusion Reactions

Details of medications to treat infusion reactions will be collected at all study visits.

3.5.1.2.8 Study Drug Administration

Weight of the IV bag/line, dates and times will be captured for each infusion of the study drug. Study drug infusion details will also include whether the infusion was interrupted or re-started along with the reasons for the interruption (for more administration instructions refer KAN-101-01 Pharmacy Manual).

3.5.2 Pharmacokinetic Assessments

For the secondary endpoint, blood samples will be collected for measurement of KAN-101, as specified in Appendix 6.1 [Table 8](#) (Part A) and [Table 9](#) (Part B). The timing of sampling may be altered based on the emerging PK data, and appropriately documented in database. PK concentrations data along with dosing data will be used to determine the PK parameters.

PK parameters will be calculated relative to start of the infusion (approximate duration 30 minutes), hence nominal time will be calculated in hours relative to start of infusion (in ADPC) for PK parameter summarization and determination of deviations from actual time of sample collection, e.g. end of infusion sample, 0 (+2) min, will be considered 0.5 h sample, 7 (\pm 2) min will be considered 0.62 h sample etc.

For Part A, PK parameters as outlined in [Table 1](#) will be determined for KAN-101 following single dose administration.

For Part B, PK parameters as outlined in [Table 2](#) will be determined for KAN-101 following multiple dose administration.

For non-compartmental analysis, actual sampling times relative to dosing rather than nominal times will be used in the calculation of all derived pharmacokinetic parameters, except when parameters are calculated for safety/dose escalation meetings when nominal times may be used to calculate PK parameters.

Table 1: Pharmacokinetic Parameters after Single Dose Administration (Part A) and after First Dose Administration (Part B)

Parameter	Definition	Method of Determination
C _{max}	Maximum observed plasma concentration	Obtained directly from the concentration-time data

Parameter	Definition	Method of Determination
DNC_{max}	Dose-normalized C_{max}	Obtained by dividing C_{max} by total dose administered in mg (scheduled dose will be used e.g. if dose level is 0.3 mg/kg and is subject weight is 50 kg, then dose administered will be 15 mg, DNC_{max} will be C_{max} divided by 15.
t_{max}	Time to first occurrence of C_{max}	Obtained directly from the concentration-time data
λ_z	Terminal elimination rate constant	
Terminal phase rate constant calculated by linear regression of the log-linear concentration-time curve. Only those data points judged to describe the terminal log-linear decline will be used in the regression.
 
 A minimum number of three data points in the terminal phase will be used in calculating λ_z with the line of regression starting at any post-C_{max} data point (C_{max} should not be part of the regression slope) and including C_{last}, t_{last}. The adjusted correlation coefficient (R^2 adjusted) in general should be greater than 0.90. Any value less than 0.90 may be used at the PK Scientist's best knowledge and judgment. An appropriate number of decimal places should be used for λ_z to enable the reported value of $t_{1/2}$ to be calculated.
$t_{1/2}$	Terminal elimination half-life	$\text{Log}_e(2) / \lambda_z$
AUC_{0-t}	AUC from time zero to the last quantifiable concentration	
The linear-log trapezoidal method will be employed to calculate AUCs. The linear method will be used for all incremental trapezoids arising from increasing concentrations and the logarithmic trapezoidal method will be used for those arising from decreasing concentrations.
 $AUC_{0-t} = \int_0^t C(t) dt.$
$DNAUC_{0-t}$	Dose normalized AUC_{0-t}	Obtained by dividing AUC_{0-t} by total dose administered in mg (scheduled dose will be used e.g. if dose level is 0.3 mg/kg and is subject weight is 50 kg, then dose administered will be 15 mg, $DNAUC_{0-t}$ will be AUC_{0-t} divided by 15.
AUC_{0-inf}	AUC from time zero extrapolated to infinity	$AUC_{0-inf} = \int_0^t C(t) dt + \int_t^\infty C(t) dt = AUC_{0-t} + C_{last} / \lambda_z,$ 
where C_{last} is last observed quantifiable concentration.

$DNAUC_{0-inf}$	Dose normalized AUC_{0-inf}	Obtained by dividing AUC_{0-inf} by total dose administered in mg (scheduled dose will be used e.g. if dose level is 0.3 mg/kg and is subject weight is 50 kg, then dose administered will be 15 mg, $DNAUC_{0-inf}$ will be AUC_{0-inf} divided by 15.
$\%AUC_{ex}$	Percentage of $AUC_{(0-inf)}$ obtained by extrapolation	$(1 - [AUC_{0-t} / AUC_{0-inf}]) \times 100$

Parameter	Definition	Method of Determination
CL	Clearance following intravenous administration	dose/AUC _{0-inf}
V _z	Volume of distribution during terminal phase	CL/F/λ _z

Table 2: Pharmacokinetic Parameters on Day 7 after Multiple Dose Administration (Part B)

Parameter	Definition	Method of Determination
C _{max}	Maximum observed concentration	Obtained directly from the concentration-time data
DNC _{max}	Dose normalized C _{max}	Obtained by dividing C _{max} by total dose administered in mg (scheduled dose will be used e.g. if dose level is 0.3 mg/kg and is subject weight is 50 kg, then dose administered will be 15 mg, DNC _{max} will be C _{max} divided by 15.
C _{min}	Minimum observed concentration	Obtained directly from the concentration-time data
t _{max}	Time corresponding to occurrence of C _{max}	Obtained directly from the concentration-time data
λ _z	Terminal elimination rate constant	Terminal phase rate constant calculated by linear regression of the log-linear concentration-time curve. Only those data points judged to describe the terminal log-linear decline will be used in the regression. A minimum number of three data points in the terminal phase will be used in calculating λ _z with the line of regression starting at any post- C _{max} data point (C _{max} should not be part of the regression slope) and include C _{last} , t _{last} . The adjusted correlation coefficient (R ² adj) in general should be greater than 0.90. Any value less than 0.90 may be used at the PK Scientist's best knowledge and judgment. An appropriate number of decimal places should be used for λ _z to enable the reported value of t _{1/2} to be calculated.
t _{1/2}	Terminal elimination half-life	Loge(2)/ λ _z
AUC _{0-t}	AUC from time zero to the last quantifiable concentration	The linear-log trapezoidal method will be employed to calculate AUCs. The linear method will be used for all incremental trapezoids arising from increasing concentrations and the logarithmic trapezoidal method will be used for those arising from decreasing concentrations. $AUC_{0-t} = \int_0^t C(t) dt.$

Parameter	Definition	Method of Determination
DNAUC _{0-t}	Dose normalized AUC _{0-t}	Obtained by dividing AUC _{0-t} by total dose administered in mg (scheduled dose will be used e.g. if dose level is 0.3 mg/kg and is subject weight is 50 kg, then dose administered will be 15 mg, DNAUC _{0-t} will be AUC _{0-t} divided by 15.
AUC _{0-inf}	AUC from time zero extrapolated to infinity	$AUC_{0-inf} = \int_0^t C(t)dt + \int_t^{\infty} C(t)dt = AUC_{0-t} + C_{last}/\lambda_z$, where C _{last} is last observed quantifiable concentration.
DNAUC _{0-inf}	Dose normalized AUC _{0-inf}	Obtained by dividing AUC _{0-inf} by total dose administered in mg (scheduled dose will be used e.g. if dose level is 0.3 mg/kg and is subject weight is 50 kg, then dose administered will be 15 mg, DNAUC _{0-inf} will be AUC _{0-inf} divided by 15.
%AUC _{ex}	Percentage of AUC _(0-inf) obtained by extrapolation	$(1 - [AUC_{0-t}/AUC_{0-inf}]) \times 100$
AUC _{0-τ}	AUC over the dosing interval	Linear-log trapezoidal method; all incremental trapezoids arising from increasing concentrations and the logarithmic trapezoidal method will be used for those arising from decreasing concentrations.
DNAUC _{0-τ}	Dose normalized AUC _{0-τ}	Obtained by dividing AUC _{0-τ} by total dose administered in mg (scheduled dose will be used e.g. if dose level is 0.3 mg/kg and is subject weight is 50 kg, then dose administered will be 15 mg, DNAUC _{0-τ} will be AUC _{0-τ} divided by 15.
CL	Clearance following intravenous administration	dose/AUC _{0-τ}
V _z	Volume of distribution during terminal phase	CL/F/λ _z
C _{av}	Average concentration	AUC _{0-τ} /τ
PTF	Peak trough fluctuation	(Mean C _{max}) / (Mean C _{min})
Rac	Accumulation ratio	Calculated from AUC _{0,τ} and AUC _{0,τ} after first dose of the multiple dosing regimen
L	Linearity index	Calculated from AUC _{0,τ} and AUC _{0-inf} after first dose of the multiple dosing regimen

Day 7 parameters will be calculated relative to that day's dosing. The value of τ will be 72 hours since dosing in Part B is 3 days apart. All above parameters will be calculated but only relevant parameters will be reported in tables, figures and listings, as per the PK scientist's evaluation of the parameters.

Following single or multiple dose administration, other PK parameters, e.g. t_{last} and partial area under the curve may be derived, if needed, but may not be reported.

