10.5. Infusion-Related Reactions

If an IRR occurs during KAN-101 administration, the following treatment recommendations are provided and may be modified per local treatment standards and guidelines as appropriate.

- Grade 1 (mild): Infusion rate modification not indicated. Administer symptomatic treatment (eg, antihistamines, antipyretics, antiemetics) as needed. Closely monitor patient until resolution. Prophylaxis with diphenhydramine 50 mg (or equivalent) and/or acetaminophen/paracetamol 325 to 1000 mg is recommended at least 30 min prior to future KAN-101 infusions
- Grade 2 (moderate): Slow infusion to $\leq 50\%$ of the original infusion rate and treat symptoms with appropriate medical therapy, including but not limited to antihistamines, antipyretics, and analgesics. Increase monitoring of vital signs as medically indicated until patient is deemed stable. Prophylaxis with diphenhydramine 50 mg (or equivalent) and/or acetaminophen/paracetamol 325 to 1000 mg is recommended at least 30 min prior to future KAN-101 infusions
- Grade 3 (severe): Stop infusion and institute appropriate symptom-directed therapy, including but not limited to antihistamines, antipyretics, corticosteroids, bronchodilators, and O₂. Increase monitoring of vital signs as medically indicated until patient is deemed stable. If the reaction has not resolved within 6 hours, the remainder of the infusion will not be administered and KAN-101 will be permanently discontinued. Following the completion or termination of a restarted infusion due to an IRR, all patients must be monitored until resolution of symptoms or for 2 hours in the absence of additional symptoms. Prophylaxis with diphenhydramine 50 mg (or equivalent) and/or acetaminophen/paracetamol 325 to 1000 mg is required at least 30 min prior to future KAN-101 infusions. The next infusion should initiate at a rate of 2 hours per dose, or 50% of the rate at which the reaction occurred. If no IRRs are observed within the first 30 minutes, the infusion rate may increase to the 1-hour-per-dose rate as outlined in [Section 10.2](#). Permanently discontinue KAN-101 upon a second occurrence of a Grade 3 or greater infusion reaction.

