12.4. KAN-101 Exposure

The summary statistics of exposure will be tabulated by study part and by dose group. In the summary, the following will be included:

- the cumulative number of days of exposure
- the number of IV infusions completed
- the relative dose intensity

All variables are predefined:

- The relative dose intensity is defined as the percentage of the planned treatments completed. It is the ratio of the cumulative actual dose (mg) and cumulative planned dose (mg) times 100. In this definition,
- the cumulative actual dose (mg) is the sum of the actual doses (mg) that the patient receives during the study
- the cumulative planned dose (mg) is the cumulative number of days of exposure times the planned dose level (mg)

All analyses within this section will be based on the All-Treated Set unless otherwise specified.

CCI

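### SAP Tables 1 and 2 divide dose-normalised Cmax and AUC by the scheduled dose, with no exception for incomplete infusions, so a partial infusion understates dose-normalised AUC

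*SAP*

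**What the plan says.** **Divisor.** In SAP 3.5.2, Table 1 (single or first dose), dose-normalised Cmax is divided by what is labelled the administered dose in mg, qualified in brackets: "scheduled dose will be used e.g. if dose level is 0.3 mg/kg". The example takes a 50 kg patient and concludes "then dose administered will be 15 mg". The AUC rows carry the same rule: "Obtained by dividing AUC_{0-t} by total dose administered in mg (scheduled dose will be used". Table 2 repeats it for Day 7 of Part B, including AUC over the dosing interval.

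**Clearance.** CL is dose over AUC (to infinity in Table 1, over the dosing interval in Table 2), and Vz is built from CL. Neither row says which dose is meant.

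**Incomplete infusions.** Protocol 10.5 provides, for a Grade 3 reaction not resolved within 6 hours, that "the remainder of the infusion will not be administered and KAN-101 will be permanently discontinued". For Grade 4 the infusion is stopped and treatment ends. SAP 3.2 has replacement rules for patients who do not receive the full dose or all three doses.

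**Who is analysed.** The PK analysis set (SAP 4.6) requires one dose of KAN-101 and one concentration value. SAP section 4 removes from PK summaries only patients whose dose level is unknown.

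**Data on the delivered amount.** SAP 3.5.1.2.8: "Weight of the IV bag/line, dates and times will be captured for each infusion of the study drug". Interruptions and their reasons are recorded too. Protocol 12.4 already needs a delivered amount for relative dose intensity: "the cumulative actual dose (mg) is the sum of the actual doses (mg) that the patient receives during the study".

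**Use.** SAP 4.9.2.1 plans no formal dose-proportionality assessment, only box plots of Cmax and AUCs and of their dose-normalised versions.

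**The concern.** The label and the bracket describe the same quantity only when the whole infusion is delivered. When it is not, the bracket governs and the parameter is divided by a dose that the patient did not receive. Dose normalisation is the step that should correct for a smaller delivered amount, and this rule prevents that.

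The error runs in one direction: an incompletely dosed patient appears to have less exposure per mg. It also sits badly with the SAP's own reasoning, which leaves out patients of unknown dose level because their PK results cannot be interpreted. PK is the secondary endpoint, and the dose-normalised values are part of how the report will show whether exposure rises in line with dose.

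**Working it through.** **1. The plan's own figure.** Dose level × weight = 0.3 mg/kg × 50 kg = 15 mg. This reproduces the SAP example and confirms that the divisor is the scheduled dose D.

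**2. One patient.** The fraction delivered, f, is not in the documents, so f = 0.90, 0.75, 0.50 and 0.25 are assumptions. Under linear PK, AUC is proportional to the delivered dose f × D. Then:
- AUC / D = f × the correct value, an understatement of 1 − f.
- AUC / (f × D) = the correct value.
- CL = D / AUC = (1/f) × the correct value, but only if D is also used there.

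In the SAP example the delivered dose would be 15 × f = 13.5, 11.25, 7.5 or 3.75 mg, against a divisor of 15 mg.

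**3. One affected patient in a group of n.** The geometric mean is multiplied by f^(1/n). The group sizes are n = 3 (a Part A cohort without expansion), n = 6 (KAN-101 patients in a Part B cohort) and n = 9 (3 + 6, the Day 1 pooling of a dose common to both parts under SAP 4.9.2). For example, 0.5^(1/3) = 0.794, a fall of 20.6%.

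| f | Patient's AUC/D understated by | Fall in geometric mean, n = 3 | n = 6 | n = 9 |
|---|---|---|---|---|
| 0.90 | 10% | 3.5% | 1.7% | 1.2% |
| 0.75 | 25% | 9.1% | 4.7% | 3.1% |
| 0.50 | 50% | 20.6% | 10.9% | 7.4% |
| 0.25 | 75% | 37.0% | 20.6% | 14.3% |

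**4. Does the delivered dose also repair dose-normalised Cmax?** Illustration: one compartment and a constant-rate 30-minute infusion stopped at f × 30 minutes. Cmax relative to a full infusion is

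r = (1 − exp(−k × f × 30)) / (1 − exp(−k × 30)), with k = ln 2 / half-life.

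The rationale for protocol amendment 4 puts the half-life below 20 minutes, so 20 and 10 minutes were tried. At f = 0.5:
- Half-life 20 min: r = 0.627 with the scheduled dose; r / f = 1.254 with the delivered dose.
- Half-life 10 min: r = 0.739 with the scheduled dose; r / f = 1.478 with the delivered dose.

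Dividing by the delivered dose therefore turns an understatement (0.63 to 0.74 of the full-infusion value) into an overstatement (1.25 to 1.48). With so short a half-life, concentration is already levelling off during the infusion, so Cmax is not proportional to the amount delivered when the infusion is cut short.

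**The case against.** The case for leaving this alone has several parts, and much of it stands.

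- **Little rests on these values.** A reader might infer that the dose-normalised parameters are the sole basis for judging dose proportionality. They are not: SAP 4.9.2.1 plots un-normalised Cmax and AUCs as well, and the assessment is informal. A box plot shows the median and spread, so one low value may simply appear as a low point, and the geometric-mean shifts do not describe the plot directly. However, a partial dose also lowers the un-normalised values, so those plots do not supply the missing correction.
- **Clearance.** A reader might infer that CL is doubled when half the dose is given. The scheduled-dose wording is attached only to the dose-normalised rows, and SAP 3.5.2 says that dosing data will be used for the PK parameters. The dose entering CL is unstated, so the overstatement is conditional.
- **The trigger is narrow.** Slowed infusions, and those restarted and completed, deliver the full dose, so the divisor is right for them. A related Grade 3 or higher reaction is a dose-limiting toxicity that pauses the study, and two at a dose level end escalation. A reader might infer a false pattern of less-than-proportional PK at higher doses. That needs partial infusions to be more frequent at higher doses, which the documents do not show, and the stopping rules limit how far it could build.
- **n = 3 is the extreme.** A replacement patient would make it 4 (0.5^(1/4) = 0.841, a 16% fall at half dose). A cohort expanded after a dose-limiting toxicity would have 6 (11%).
- **Affected values could be traced.** PK listings show actual against scheduled infusion duration (SAP 4.9.1), drug administration is listed by patient, and data review meetings can exclude data. None of these is a written rule for partial infusions, and none changes the divisor.
- **The SAP does not mention incomplete infusions in this rule.** That is true. The consequence follows because the rule is unqualified.

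**Conclusion.** The point holds as a defect in a definition. Tables 1 and 2 name one dose and prescribe another. Followed as written, the rule understates dose-normalised AUC by the undelivered fraction. For one affected patient the geometric mean shifts by 21%, 11% or 7% at half dose and by 3.5%, 1.7% or 1.2% at 90% delivered (n = 3, 6, 9).

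These figures rest on linear PK, one affected patient and an assumed f. If every infusion is complete there is no error. The reach is limited to descriptive PK output and the informal dose-proportionality plots. The primary endpoint and the calculation of un-normalised Cmax and AUC do not depend on the divisor. An effect on CL and Vz cannot be asserted, only that the SAP leaves it open. The correction is worth making because it is cheap and its raw data are already collected.

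**What to change.** In SAP Tables 1 and 2:

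- Use the delivered dose in mg as the divisor for all dose-normalised AUCs and as the dose in CL, and hence Vz. Derive it from the recorded bag/line weights, consistently with the actual dose in Protocol 12.4.
- State how a weight becomes mg. SAP 3.5.1.2.8 records the weight but gives no conversion.
- Use the scheduled dose only where weights are missing, and flag those values.
- Where an infusion was stopped early or interrupted, flag dose-normalised Cmax in the listing and leave it out of dose-normalised summaries and plots. Re-dividing it by the delivered dose would not correct it.

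The cost is SAP wording, one small derivation and a few flagged values. No new data collection is needed.
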